10.3.4. Reporting of SAEs

SAE Reporting CT SAE Report Form

- Facsimile transmission of the CT SAE Report Form is the preferred method to transmit this information to Pfizer Safety.
- In circumstances when the facsimile is not working, notification by telephone is acceptable with a copy of the CT SAE Report Form sent by overnight mail or courier service.
- Initial notification via telephone does not replace the need for the investigator to complete and sign the CT SAE Report Form pages within the designated reporting time frames.

10.4. Appendix 4: Contraceptive Guidance and Collection of Pregnancy Information

To avoid the transmission of vector-related material and pregnancy, all sexually active participants are required to 1 of the following acceptable forms of contraceptives during the study until at least 3 consecutive post-treatment semen samples are negative for AAV2/6 and for a minimum of 90 days after SB-525 (PF-07055480) administration:

- Double barrier contraceptive including use of a condom plus one other form of contraception used by the participant or partner (eg, vasectomy, intrauterine device [IUD], birth control pills, and diaphragm with spermicide).
- A condom must be used for any form of sexual activity to prevent the transmission of vector-related material.
- Sexual abstinence.

Pregnancies of a partner should be recorded using the Pregnancy Initial Report Form. Pregnancies should be followed until final outcome is known. All follow-up for a pregnancy should be submitted on a Pregnancy Follow-up Report Form.

10.5. Appendix 5: Genetics

Use/Analysis of DNA

- Genetic variation may impact a participant's response to study intervention, susceptibility to, and severity and progression of disease. Therefore, where local regulations and IRB/IEC allow, a blood sample will be collected for DNA analysis.
- The results of genetic analyses may be reported in the CSR or in a separate study summary, or may be used for internal decision-making without being included in a study report.
- The sponsor will store the DNA samples in a secure storage space with adequate measures to protect confidentiality.

10.6. Appendix 6: Liver Safety: Suggested Actions and Follow-up Assessments

Potential Cases of Drug Induced Liver Injury

Humans exposed to a drug who show no sign of liver injury (as determined by elevations in transaminases) are termed “tolerators,” while those who show transient liver injury, but adapt are termed “adaptors”. In some participants, transaminase elevations are a harbinger of a more serious potential outcome. These participants fail to adapt and therefore are “susceptible” to progressive and serious liver injury, commonly referred to as drug-induced liver injury (DILI). Participants who experience a transaminase elevation above $3 \times$ ULN should be monitored more frequently to determine if they are an “adaptor” or are “susceptible”.

In the majority of DILI cases, elevations in AST and/or ALT precede total bilirubin (TBili) elevations ($>2 \times$ ULN) by several days or weeks. The increase in TBili typically occurs while AST/ALT is/are still elevated above $3 \times$ ULN (ie, AST/ALT and TBili values will be elevated within the same lab sample). In rare instances, by the time TBili elevations are detected, AST/ALT values might have decreased. This occurrence is still regarded as a potential DILI. Therefore, abnormal elevations in either AST **OR** ALT in addition to TBili that meet the criteria outlined below are considered potential DILI (assessed per Hy’s law criteria) cases and should always be considered important medical events, even before all other possible causes of liver injury have been excluded.

The threshold of laboratory abnormalities for a potential DILI case depends on the participant’s individual baseline values and underlying conditions. Participants who present with the following laboratory abnormalities should be evaluated further as potential DILI (Hy’s law) cases to definitively determine the etiology of the abnormal laboratory values:

- Participants with AST/ALT and TBili baseline values within the normal range who subsequently present with AST **OR** ALT values $>3 \times$ ULN AND a TBili value $>2 \times$ ULN with no evidence of hemolysis and an alkaline phosphatase value $<2 \times$ ULN or not available;
- For participants with baseline AST **OR** ALT **OR** TBili values above the ULN, the following threshold values are used in the definition mentioned above, as needed, depending on which values are above the ULN at baseline:
 - a. Preexisting AST or ALT baseline values above the normal range: AST or ALT values >2 times the baseline values AND $>3 \times$ ULN; or $>8 \times$ ULN (whichever is smaller).
 - b. Preexisting values of TBili above the normal range: TBili level increased from baseline value by an amount of at least $1 \times$ ULN or if the value reaches $>3 \times$ ULN (whichever is smaller).

Rises in AST/ALT and TBili separated by more than a few weeks should be assessed individually based on clinical judgment; any case where uncertainty remains as to whether it represents a potential Hy’s law case should be reviewed with the sponsor. The participant should return to the investigator site and be evaluated as soon as possible, preferably within

48 hours from awareness of the abnormal results. This evaluation should include laboratory tests, detailed history, and physical assessment.

In addition to repeating measurements of AST and ALT and TBili for suspected cases of Hy's law, additional laboratory tests should include albumin, CK, direct and indirect bilirubin, GGT, PT/INR, total bile acids, and alkaline phosphatase. Consideration should also be given to drawing a separate tube of clotted blood and an anticoagulated tube of blood for further testing, as needed, for further contemporaneous analyses at the time of the recognized initial abnormalities to determine etiology. A detailed history, including relevant information, such as review of ethanol, acetaminophen/paracetamol (either by itself or as a coformulated product in prescription or over-the-counter medications), recreational drug, supplement (herbal) use and consumption, family history, sexual history, travel history, history of contact with a jaundiced person, surgery, blood transfusion, history of liver or allergic disease, and potential occupational exposure to chemicals, should be collected. Further testing for acute hepatitis A, B, C, D, and E infection and liver imaging (eg, biliary tract) and collection of serum samples for acetaminophen/paracetamol drug and/or protein adduct levels may be warranted.

All cases demonstrated on repeat testing as meeting the laboratory criteria of AST/ALT and TBili elevation defined above should be considered potential DILI (Hy's law) cases if no other reason for the LFT abnormalities has yet been found. **Such potential DILI (Hy's law) cases are to be reported as SAEs, irrespective of availability of all the results of the investigations performed to determine etiology of the LFT abnormalities.**

A potential DILI (Hy's law) case becomes a confirmed case only after all results of reasonable investigations have been received and have excluded an alternative etiology.

10.7. Appendix 7: Safety Monitoring and Mitigation Plan

The liver function (AST, ALT, bilirubin, alkaline phosphatase, and GGT) of study participants will be monitored closely throughout the study.

Based on preclinical evidence, SB-525 (PF-07055480) has the potential to deliver effective FVIII activity at low administered AAV doses, thus avoiding the transaminitis observed with other gene therapy products at higher AAV doses. For this reason, routine steroid prophylaxis is not planned for initial doses or any dose levels. This study, however, will closely monitor LFT (at least twice weekly through the second LTF determination during Week 20 following dosing) and FVIII activity (at least weekly for through Week 20) after dosing to assess for any potential transaminitis and/or effects on FVIII activity. Steroid treatment will be initiated (recommended: prednisone 60 mg daily or equivalent) in any participant who experiences an ALT increase $>1.5 \times$ baseline level after dosing with SB-525 (PF-07055480). Note that the baseline ALT levels will be determined by the central laboratory with subsequent LFTs (ALT and AST at a minimum) performed by the local laboratories for safety. Additionally, steroid treatment may not be initiated if medically contraindicated.

In the case of ALT elevation requiring steroid, LFTs will continue to be followed twice weekly, and steroids will continue to be dosed until the ALT value has stabilized (3 consecutive values under the ULN with no increase of ALT). At that point, if steroids were taken for more than 3 weeks, a steroid taper, with close laboratory monitoring, can be initiated per the following table:

	Week 1	Week 2	Week 3	Week 4
Prednisone	60 mg/day	30 mg/day	15 mg/day	5 mg/day

The steroid taper can be halted and the dosing reverted at any time to a higher prednisone dose if the 3 consecutive values of ALT are not decreasing to baseline and/or ALT values are above the ULN. If 3 consecutive values are below the ULN but have not fully returned to baseline, the taper can continue after discussion with the medical monitor. Refer to SoA Table ([Table 1](#)).

Routine steroid prophylaxis will be considered for all current and future dose levels if ALT elevation is observed in 2 participants above $1.5 \times$ ULN, or, above $5 \times$ ULN in 1 participant. DMC will be contacted or convened appropriately. The regulatory authorities will be notified and will review plans if prophylaxis implementation is planned. Note that while ALT changes from baseline will guide decisions to initiate steroid therapy within an individual, changes above the ULN will guide criteria to convene the DMC or decide future prophylactic steroid recommendations. If warranted, the prophylactic steroid regimen would be defined by the DMC in concert with the sponsor.

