Table 1. Schedule of Activities

Procedure	Screening	Baseline ^a	Infusion Center		Day 7 (±1 day)	Weeks 2, 4, 6, 8, 10, 12 (±3 days)	Weeks 16, 20, 24, 28, 32, 36, 40, 44, 48, 52 (±1 wk)	Months 24, 36, 48, 60 (±1 M)	Early Termination Visit
			Day 0 ^b	Day 1					

- i. Both local and central LFTs will be performed. At Screening, liver panel will be performed twice, at least 1 week apart. Following infusion, LFTs will be done twice a week from the first collection approximately 3 to 4 days after Day 0 and continuing until Week 20. The local laboratory results may be utilized for the investigator to react promptly if an ALT elevation occurs. Note: Local and central LFTs are drawn tandemly twice weekly.
- j. Continue central and local LFT assessments twice per week if participant is receiving steroids. LFT assessments will continue twice weekly until 3 consecutive results demonstrate stable liver function. At this time LFT assessment may be decreased to once a week.
- k. If a participant has FVIII administration around the day of a visit when FVIII activity is scheduled, sample collection should be postponed at least 48 or 72 hours based on the FVIII product used (short half-life or long half-life, respectively).
- l. If a participant is receiving steroids or if a participant develops an inhibitor, weekly assessments of FVIII activity, FVIII antigen and FVIII inhibitor titer will continue.
- m. Central and local FVIII activity assessment will be performed. After Week 52, measurement of FVIII activity will be done every 6 months, and may increase if warranted by changes in FVIII activity or presence of inhibitor. Mobile phlebotomy can be used as needed.
- n. Central FVIII inhibitor titer assessment will be conducted. After Week 52, measurement of FVIII inhibitor titer may increase if warranted by changes in FVIII activity or the presence of inhibitor.
- o. Vector genomes in plasma, saliva, urine, stool, and semen by PCR (unless three previous consecutive specimens have been negative, see footnote p). On Day 0, vector genome titer should be obtained in **plasma only** at 12 hours from the start of the infusion ± 1 hour.
- p. Collection will only continue until three consecutive negative samples are obtained on a sample-type basis and every 1 month after Week 52 to Month 60 [±1 month]). For example, after urine sample results are negative 3 consecutive times, the urine sample will stop being collected while the other samples may continue if they are positive.

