4.2. Scientific Rationale for Study Design

Hemophilia is an attractive target for gene therapy. This is due in part because minute-to-minute regulation of FVIII/Factor IX clotting protein (FIX) expression is not required (unlike proteins such as insulin). In addition, there is a wide therapeutic window for FVIII/FIX expression since therapeutic benefit can be achieved in severe hemophiliacs, who have FVIII/FIX activity <1%, with only modest improvements in factor expression. Any factor activity over 1% results in an improved phenotype (moderate hemophilia 1-5% or mild hemophilia 5-40%).

As the study was being planned, 1 adeno-associated virus (AAV)-mediated FVIII cDNA- and 5 AAV-mediated FIX cDNA-gene-transfer studies have been initiated and have reported at least some clinical study data. Details are provided in the Investigator's Brochure. Of the various AAV serotypes tested in the clinic, none have utilized the AAV6 serotype that will be tested in this clinical trial. Of the 4 studies where gene therapy was delivered intravenously, factor protein expression generally exhibited a dose response, though peak expression and durability of effect have been variable. Alanine aminotransferase (ALT) elevations due to AAV-associated transaminitis have been observed in at least 1 dose level in all studies reported to date using the IV route. AAV-associated transaminitis has been reported at vector doses ranging from 5×10^{11} vg/kg to 6×10^{13} vg/kg, with variable amount of losses in factor protein expression that may be associated with time to initiation of steroid therapy. Additional information on AAV-associated transaminitis is provided in Section [10.7](#).

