10.2. Appendix 2: Clinical Laboratory Tests

The following safety and efficacy laboratory tests will be performed at times defined in the SoA ([Table 1](#)).

Additional laboratory results may be reported on these samples as a result of the method of analysis or the type of analyzer used by the clinical laboratory, or as derived from calculated values. These additional tests would not require additional collection of blood. Unscheduled clinical laboratory measurements may be obtained at any time during the study to assess any perceived safety issues.

The tests detailed below will be performed by the Central Laboratory (CL) unless otherwise indicated Local Laboratory (LL).

Hematology (CBC with Differential and Platelet Count) - Safety

Platelet Count	RBC Indices:	Automated WBC Differential (absolute and percent):
RBC Count	MCV	Neutrophils
WBC Count (absolute)	MCH	Lymphocytes
Hemoglobin	MCHC	Monocytes
Hematocrit		Eosinophils
Reticulocytes		Basophils

Clinical Chemistry - Safety

Serum Chemistry	Liver Function Tests (CL and LL)
Blood Urea Nitrogen	AST (SGOT)
Creatinine	ALT (SGPT)
Glucose	GGT
Sodium	Alkaline phosphatase
Potassium	Total and direct bilirubin
Chloride	
Total CO ₂	
Calcium, Magnesium, Phosphate	
Uric Acid	
Albumin	
Total Protein	
Lactate dehydrogenase	

Factor VIII activity (CL and LL)

Central FVIII activity assessed by both chromogenic and one-stage assays
Local FVIII activity assessed by chromogenic or one-stage assays

Immunogenicity

Anti-AAV2/6 antibodies (neutralizing and total)
FVIII inhibitor testing
T-cell responses specific to AAV2/6 and FVIII by ELISPOT assay

Vector Shedding

Detection of AAV2/6 vector by PCR in plasma, saliva, urine, stool and semen

Urinalysis - Safety

Specific gravity
pH, glucose, protein, blood and ketones
Blood or protein if >trace positive
Microscopic exam if macroscopic blood or protein is small (1+), moderate (2+), or large (3+)

Exploratory Parameters

Study drug mechanism of action and immune responses: including but not limited to IL6, CRP, soluble epidermal growth factor receptor (sEGFR), galectin-3-binding protein (Gal3BP), C-reactive protein (CRP)
FVIII antigen
vWF

Other Parameters

HIV RNA viral load and HIV 1/2 antibody assay - screening only
Hepatitis B panel, hepatitis C virus antibody, and HCV RNA viral load – screening only
Coagulation parameters: PT, aPTT, INR
Circulating alpha fetoprotein
FVIII gene sequencing

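### The individual steroid trigger (ALT >1.5 x baseline) takes its baseline from the central laboratory and its follow-up from local ones; acting on a local value before the paired central result arrives moves the threshold to 1.5/f

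*Protocol*

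**What the plan says.** Protocol Appendix 7 (section 10.7) starts steroids, with prednisone 60 mg daily or equivalent recommended, "in any participant who experiences an ALT increase $>1.5 \times$ baseline level after dosing". A note attached to that rule says that "baseline ALT levels will be determined by the central laboratory with subsequent LFTs (ALT and AST at a minimum) performed by the local laboratories"; it gives safety as the purpose of the local tests. The same appendix separates two yardsticks: "ALT changes from baseline will guide decisions to initiate steroid therapy within an individual", while multiples of the upper limit of normal (ULN) decide when the DMC is involved and whether prophylactic steroids are considered.

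The Schedule of Activities (Protocol section 1.3, footnote i) adds three facts:

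- On which laboratories test: "Both local and central LFTs will be performed. At Screening, liver panel will be performed twice, at least 1 week apart".
- On pairing of samples after dosing: "Note: Local and central LFTs are drawn tandemly twice weekly".
- On what may be acted on: "The local laboratory results may be utilized for the investigator to react promptly if an ALT elevation occurs".

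Protocol Appendix 2 also lists liver function tests for both laboratories. SAP section 6.6.2 summarises central liver data and only lists the local values.

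Neither document gives a local-to-central conversion, names a local baseline for the trigger, requires the central result to confirm a local one, or says what to do when the two disagree.

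**The concern.** A change-from-baseline rule is safe against laboratory differences only if both values come from the same laboratory. Here the note that goes with the trigger assigns the two values to different laboratories. An investigator who follows the note and uses the fast local result, as footnote i allows, divides a local number by a central one. Any systematic difference between the assays then enters the ratio, and it may differ from site to site.

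An error costs something in either direction. If the local assay reads high, a smaller true rise starts high-dose prednisone. If it reads low, a larger rise is needed first, and Protocol section 4.2 reports from earlier gene-transfer studies "losses in factor protein expression that may be associated with time to initiation of steroid therapy". FVIII activity is a primary endpoint in this trial, so late treatment is not a side issue. Acting on fast local results is therefore sensible. The weak point is only the baseline against which they are judged.

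**Working it through.** **Inputs.** From the documents: the threshold of 1.5 times baseline and the laboratory assignment (Appendix 7), and twice-weekly paired local and central draws to Week 20, about 40 draws (footnote i). Assumed, because the documents do not give them: the offset f, defined as local divided by central on the same sample, and all coefficients of variation (CVs). The trigger is read as follow-up ALT exceeding 1.5 times baseline ALT.

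**Threshold.** Let C0 and Ct be the central values at baseline and follow-up, and let the local follow-up be f x Ct. The mixed rule fires when

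f x Ct > 1.5 x C0, that is, Ct/C0 > 1.5/f.

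At f = 1 this returns the stated 1.5. Otherwise:

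| f (assumed) | 1.5/f = true rise needed |
|---|---|
| 0.8 | 1.88 |
| 0.9 | 1.67 |
| 1.0 | 1.50 |
| 1.1 | 1.36 |
| 1.2 | 1.25 |

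If the offset is additive, say plus or minus 5 U/L at a baseline of 30 U/L, the threshold is (45 - 5)/30 = 1.33 or (45 + 5)/30 = 1.67. With both values from one laboratory, a proportional f cancels and the threshold is 1.5 whatever f is. Without any true rise or random variation, an offset alone would fire the rule only if f exceeded 1.5.

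**Illustration of chance crossings.** Log-normal simulation of 60,000 participants with 40 draws each and no true rise. Assumptions: within-person CV 10%, shared by paired samples; analytic CV 5%, independent by laboratory; a single baseline value. Chance of at least one ratio above 1.5:

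| f | local/central | local/local | local/central and paired central/central both above 1.5 |
|---|---|---|---|
| 0.9 | 1.5% | 9% | 1.4% |
| 1.0 | 9% | 9% | 5.2% |
| 1.1 | 29% | 9% | 8.3% |
| 1.2 | 55% | 9% | 9.1% |

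The levels depend heavily on the assumed CV: the local/local figure is 3% at a within-person CV of 8% and 35% at 15%.

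**Illustration of a real rise.** For a true 1.6-fold rise and one draw under the same CVs, the log-scale standard deviation of the ratio is s = sqrt(2 ln 1.01 + 2 ln 1.0025) = 0.158. The chance of crossing is 1 - Phi((ln 1.5 - ln(1.6 f))/s), which gives 40%, 66% and 84% at f = 0.9, 1.0 and 1.1. The same-laboratory ratio gives 66% throughout.

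**The case against.** The strongest reply is that the like-for-like data are already collected. Each local value in the intensive period has a paired central value that can be set against the central baseline. Use of local results is optional, and the Appendix 7 note says who runs the tests; it does not say that the trigger is computed as local divided by central. This stands. A reader might infer that the protocol mandates a mixed ratio, but the text does not say so. The exposure is limited to decisions taken before the paired central value arrives, and the documents do not state that turnaround time. What remains is that nothing requires the central check, and waiting for it gives up the prompt reaction that footnote i is there to allow.

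A second reply is that no size can be taken from the documents. This also stands. A reader might take the 29% or 55% above as the expected rate of unnecessary steroid courses. Those figures need a persistent local-high offset, assumed CVs, and a steroid start at every single crossing without a look at the paired central value. Requiring that value to agree brings 29% down to about 8%.

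Third, the reach is limited. The start of the taper, the DMC contact and the prophylaxis decision rest on the ULN. Baseline re-enters only when a taper is reviewed, alongside the ULN. Steroids may be withheld if contraindicated. A reader might suspect that the analysis tables are distorted too, but the liver summaries use central data only.

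**Conclusion.** The point holds in a limited form. Read together, Appendix 7 and footnote i permit a local follow-up value to be judged against a central baseline, and when that happens the effective threshold is 1.5/f and not 1.5. The algebra is exact for a proportional offset. Its size in this trial is unknown because f is not in the documents: there is no shift at f = 1, and the 10% and 20% ranges are assumptions. The simulated percentages show direction and sensitivity only.

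The documents do not support a claim that the mixed ratio is prescribed, that steroid starts are known to be mistimed, or that liver monitoring is inadequate. The rule can perform worse than intended, and one sentence would prevent it. This is a cheap improvement of low severity.

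**What to change.** State in Appendix 7 that the individual trigger compares follow-up and baseline ALT from the same laboratory. The default is local follow-up over a recorded pre-dose local value. Footnote i suggests that such a value exists, since both laboratories run liver tests, but it does not expressly place a local panel at the baseline visit, so the text should ask for one. Where no local pre-dose value exists, use the paired central follow-up over the central baseline. That branch gives up the speed of the local result, and the wait should be accepted openly.

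The 1.5 threshold and the sampling schedule after dosing stay as they are. The costs are one recorded local baseline per participant and somewhat more chance crossings than under the mixed ratio at sites whose assay reads below central (9% against 1.5% at f = 0.9 in the illustration). That is the price of restoring the intended threshold there. Requiring the paired central ratio to confirm a local crossing is a reasonable alternative if the sponsor prefers one common central baseline, but it delays every start until the central result is in.

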5.2. Exclusion Criteria

Participants are excluded from the study if any of the following criteria apply:

1. Neutralizing activity to AAV6 capsid.
2. Current inhibitor, or history of FVIII inhibitor (except for transient low titer inhibitor detected in childhood).
3. History of hypersensitivity response to FVIII.
4. History of hepatitis B or HIV-1/2 infection.
5. History of hepatitis C, unless viral assays in 2 samples, collected at least 6 months apart, are negative.
6. Two (2) or more occurrences of any of the following: hemoglobin <10g/dL, platelets <100,000/ μ L, or white blood cells less than 4,000 cells/ μ L.
7. Evidence of any bleeding disorder in addition to hemophilia A.
8. History of tuberculosis or systemic fungal disease.
9. Symptomatic cardiovascular disease as a co-morbid condition.
10. Markers of hepatic inflammation or overt or occult cirrhosis as evidenced by 1 or more of the following:
 - Albumin \leq 3.5 g/dL;
 - Total bilirubin $>$ 1.5 x ULN and direct bilirubin \geq 0.5 mg/dL;
 - Alkaline phosphatase $>$ 2.0 \times ULN;
 - ALT or aspartate aminotransferase (AST) $>$ 1.3 \times ULN;
 - International Normalized Ratio (INR) $>$ 1.5.
11. History of chronic renal disease or creatinine \geq 1.5 mg/dL.
12. Use of systemic (IV or oral) immunomodulatory agent or steroid use within 3 months prior to screening (inhaled or topical treatment is allowed, eg, for asthma or eczema).

13. History of chronic infection or other chronic disorder considered an unacceptable risk.
14. Presence of liver mass on magnetic resonance imaging (MRI) or any equivalent imaging technology, or, positive alpha fetoprotein.
15. Presence of >Grade 2 liver fibrosis on elastography (or any equivalent imaging technology) for participants with history of treated Hepatitis C or suspicion of chronic liver disease.
16. History of malignancy except for successfully treated basal cell carcinoma.
17. History of alcohol or substance abuse.
18. Any contraindication to the use of corticosteroids.
19. Previously received gene therapy product.
20. Participation in prior investigational drug or medical device study within 3 months prior to screening.
21. History of therapeutic non-adherence.
22. Any other reason that, in the opinion of the investigator or medical monitor, would render the participant unsuitable for participation in the study.

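### The steroid stop condition is tied to the ULN, but eligibility admits baseline ALT up to 1.3 × ULN, so an eligible participant can recover fully and still not meet it

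*Protocol*

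**What the plan says.** - **Entry.** Protocol Section 5.2, criterion 10, has an item beginning "ALT or aspartate aminotransferase (AST") with a limit of more than 1.3 × ULN. Baseline ALT above 1.0 and up to 1.3 × ULN is therefore allowed.
- **Start.** Protocol Appendix 7 (Section 10.7) starts steroids "in any participant who experiences an ALT increase" of more than 1.5 × baseline. The reference is the participant's own baseline.
- **Stop.** Once started, "steroids will continue to be dosed until the ALT value has stabilized (3 consecutive values under the ULN with no increase of ALT"). The reference is now the ULN. The taper hangs on the same condition: "At that point, if steroids were taken for more than 3 weeks, a steroid taper, with close laboratory monitoring, can be initiated".
- **Taper halt.** A taper may be stopped or reversed if three successive values are "not decreasing to baseline and/or ALT values are above the ULN".
- **Flexibility.** "If 3 consecutive values are below the ULN but have not fully returned to baseline, the taper can continue after discussion with the medical monitor".
- **Elsewhere.** Protocol Appendix 6 (Section 10.6) has a separate branch headed "Preexisting AST or ALT baseline values above the normal range" for identifying possible drug-induced liver injury. Appendix 7 has no branch of this kind.

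**The concern.** The start rule and the stop rule use different reference points, and eligibility lets the two come apart. When baseline is at or below the ULN, return to baseline generally brings ALT to a level consistent with stopping. When baseline is above the ULN, it does not: the participant can be back exactly where he entered the study and still be above the stop threshold. His usual ALT is then also a listed ground for halting or reversing a taper.

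At stake is steroid exposure that continues after the ALT rise has resolved, in a protocol whose Section 6.5 describes prednisone use as a short course. This is more than missing detail. The rule is stated, and following it as written gives this result.

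**Working it through.** The protocol offers no calculation to reproduce here, so the check compares thresholds in ULN units.

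**Inputs.** Eligibility limit 1.3 × ULN (Section 5.2). Start trigger 1.5 × baseline, and a stop condition of three successive values below 1.0 × ULN (Appendix 7). The ULN is treated as a single number. Appendix 7 takes baseline from the central laboratory and later tests from local laboratories, and does not say whose ULN applies.

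**Step 1: thresholds.** For baseline b × ULN, the start trigger is 1.5 × b. The fall below own baseline needed to reach the ULN is 1 − 1/b.

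| Baseline b | Start trigger (× ULN) | Required fall below own baseline |
|---|---|---|
| 0.8 | 1.20 | none |
| 1.1 | 1.65 | 1 − 1/1.1 = 9.1% |
| 1.2 | 1.80 | 1 − 1/1.2 = 16.7% |
| 1.3 | 1.95 | 1 − 1/1.3 = 23.1% |

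With an assumed ULN of 40 U/L, a participant at the limit enters at 1.3 × 40 = 52, starts steroids above 1.5 × 52 = 78, and must then read below 40, although full recovery for him is 52.

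**Step 2: do other clauses cover him?**
- The medical-monitor clause requires values already below the ULN that are still above baseline. That can occur only when baseline is below the ULN.
- Table 1 footnote j relaxes the frequency of liver tests once liver function is stable. It does not govern steroid dosing.
- Appendix 7 states that baseline guides the individual decision to start, and that the ULN guides DMC and prophylaxis decisions. It gives no reason for using the ULN in the individual decision to stop.

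**Step 3: how hard is the condition to meet by chance?** This is an illustration on assumptions that are not in the documents: ALT has returned to own baseline (as the median), values are lognormal with within-person CV of 10%, 20% or 30%, and draws are independent and twice weekly for 12 weeks (2 × 12 = 24 draws). With s = √ln(1 + CV²), the chance that one value is below the ULN is p = Φ(−ln b / s). For b = 1.2 and CV 20%, s = 0.198 and p = Φ(−0.92) = 0.179. The chance of at least one run of three in 24 draws follows from an exact recursion on the current run length.

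| Baseline b | CV 10% | CV 20% | CV 30% |
|---|---|---|---|
| 0.8 | ≥0.999 | ≥0.999 | 0.999 |
| 1.1 | 0.09 | 0.41 | 0.56 |
| 1.2 | 0.001 | 0.10 | 0.28 |
| 1.3 | <0.001 | 0.02 | 0.11 |

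The added requirement of no ALT increase is ignored here. Including it could only lower these figures.

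**The case against.** Requiring ALT to be under the ULN before tapering can be a deliberate, conservative choice. The affected group is also narrow: baseline within a band 0.3 × ULN wide, then a rise above 1.5 × baseline, then no run of values below the ULN. No such participant is reported. Both points stand as limits on size. Neither explains how the rule is meant to work for someone admitted with ALT already above the ULN, and Section 8 of the protocol rules out waivers.

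Several stronger readings are tempting, and the documents do not support them.

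- **The endpoint can never be reached.** Too strong. ALT can drift below baseline. In the illustration, a participant at 1.1 × ULN has a 0.41 to 0.56 chance of a qualifying run within 12 weeks at CVs of 20% to 30%.
- **The full dose must be kept, or a taper must be reversed.** The starting dose is given as a recommendation, the stop sentence says only that dosing continues, and halting or reversing a taper is permitted, not required.
- **The study-wide prophylaxis trigger has the same fault** ("Routine steroid prophylaxis will be considered for all current and future dose levels if ALT elevation is observed in 2 participants above" 1.5 × ULN). Appendix 7 explains why that trigger uses the ULN, and it leads only to consideration, with DMC contact and regulatory review of any plan. It is a disclosed choice.
- **The SAP's Cohort 4 corticosteroid summaries would be wrong.** SAP Section 6.5.4 summarises the durations that occurred. Longer courses would be reported correctly.
- **Appendix 6 supplies the answer.** It concerns case identification, and its raised-baseline branch mixes baseline and ULN multiples. It shows only that raised baselines were foreseen.

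**Conclusion.** The conflict is in the text and holds without any outside figure. A participant admitted with ALT above the ULN who recovers fully does not meet the written stop condition until ALT falls more than 9.1%, 16.7% or 23.1% below his entry level, at baselines of 1.1, 1.2 and 1.3 × ULN. He may meet it late or not at all. These percentages rest only on the stated thresholds and a common ULN. The probabilities rest on the assumed CVs and independent draws, and show direction only.

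The number affected is unknown. The point warrants correction because it concerns a safety rule stated in mandatory terms and the remedy is cheap. The start rule carries no end date, and liver panels continue every 6 months to Month 60, so the wording can still apply during follow-up.

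**What to change.** Reconcile criterion 10 of Protocol Section 5.2 with the stabilisation and taper-halt sentences of Appendix 7, so that Appendix 7 states how stabilisation is judged when an eligible baseline ALT exceeds the ULN. The same edit could state which laboratory's ULN applies. Which criterion to adopt is for the sponsor and the DMC, and none is proposed here.

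SAP Section 6.5.3 already lists four cohorts with their doses, which suggests that dosing may be finished, although the documents do not say so. If it is, changing criterion 10 would help no one already treated, and the change belongs in Appendix 7.

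Cost: an amendment to a few sentences, with no new tests, visits or participants.
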